### 7.4.3 Analysis of the Secondary Endpoint(s)

Secondary endpoints include symptoms reported over time via questionnaires, as well as other clinical endpoints such as hospital admission, ICU admission, and mortality. These binary clinical outcomes will be analyzed in a manner similar to that described above for the primary endpoint. Symptoms will be included as predictor variables. Antibody titers for SARS-CoV-2, measured as an exploratory endpoint in serum or plasma samples, will also be analyzed as binomial values. Positive values will be defined as a four-fold or greater increase in IgG antibody titers compared to baseline. Other descriptive analyses will be provided of the antibody titer results, including geometric mean, median, standard deviation, and titer range.

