## Schematic of Study Design

## 1 Background Information and Scientific Rationale

Severe acute respiratory syndrome coronavirus 2 (SARS-CoV-2) is a coronavirus novel to the human population discovered in December 2019; it is currently the cause of a global pandemic [1-3]. The World Health Organization (WHO) named the novel coronavirus severe acute respiratory syndrome coronavirus 2 (SARS-CoV-2) and the disease caused by SARS-CoV-2 coronavirus disease (COVID-19). As of 7 April 2020, person-to-person transmission has occurred worldwide, approaching 1.5 million cases and over 75,000 deaths. The WHO declared the COVID-19 pandemic a Public Health Emergency of International Concern on 30 January 2020 [4]. Most deaths and severe pneumonitis have occurred in the elderly or in persons with underlying pulmonary, cardiac, and other co-morbidities. SARS-CoV-2 infection can be asymptomatic, mild with self-limited pneumonia and other symptoms, or progress to life threatening respiratory involvement and multi-organ failure. The infection often appears less severe in children and younger adults [5]. Nevertheless, the burden to health and economic systems globally of this pandemic is already substantial and the pandemic has not peaked on a worldwide basis. No acquired immunity to this novel viral infection appears to exist in the human population globally and no effective treatment or preventative agent is licensed at this time.

An early report of 1700 cases of COVID-19 among health care workers (HCWs) caring for COVID-19 patients in China, included 5 deaths, in a published series of over 72,000 cases [6]. The number of HCWs infected with SARS-CoV-2 are increasing every day in USA and other countries.

On 3 March 2020, WHO declared a global shortage of personal protective equipment (PPE) leaving doctors, nurses and other frontline workers dangerously ill-equipped to care for COVID-19 patients [7]. By nature of their work caring for ill patients and evidence that SARS-CoV-2 can be transmitted from human-to-human, HCWs are at increased risk for COVID-19 infection. Many aerosol-generating procedures (AGP) are performed without knowing SARS-CoV-2 infection status. The SARS-CoV-2 epidemic has put tremendous strain on HCW

in all aspects. Scientists at the UNM HEALTH SYSTEMS are interested in studying the SARS-CoV-2 and strategies to protect HCWs in high-risk exposure settings.

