### 3 Objectives

Primary Objective	Primary Endpoint
To evaluate the efficacy of hydroxychloroquine (HCQ) for prophylaxis to prevent severe acute respiratory syndrome coronavirus 2 (SARS-CoV-2) infection among HCWs at high risk of occupational exposure to SARS-CoV-2 compared to eligible cohort that declines treatment	Frequency of infection with SARS-CoV-2 as determined by positive PCR for the virus on standard diagnostic tests.
Secondary Objectives	Secondary Endpoints
1. To characterize whether high-risk HCW who test positive for SARS-CoV-2 have an asymptomatic infection or report symptoms of COVID-19 in the 4 weeks preceding positive SARS-CoV-2	1. Symptom questionnaires performed once daily as currently mandated for HCW in high risk settings within UNMHS.
2. Determine role of occupational health exposure risk level on subsequent conversion frequency (mild-moderate-severe)	2. Online survey required once daily for all at risk HCW (existing document)
3. To assess the severity of any SARS-CoV-2 infection after prophylactic treatment with hydroxychloroquine.	3. Symptom questionnaires, Hospital admission rate, ICU admission rate, Mortality rate, PSI score of respiratory compromise
4. To assess the tolerability of hydroxychloroquine prophylaxis of SARS-CoV-2 in this population	4. Incidence of AEs or SAEs related to HCQ at study termination.
Exploratory Objectives	Exploratory Endpoints
1. To determine whether hydroxychloroquine reduces time lost from work	1. Days away from work
2. To assess the compliance of hydroxychloroquine prophylaxis	2. Frequency of missing dose
3. To assess whether HCQ benefits are different for specific AGPs or exposure on certain covid units (MICU v. ED v. covid rule out unit)	3. Frequency of positive test for SARS-CoV-2 related to AGP's or specific Covid-19 units.
4. To compare seroconversion between HCQ-treated and HCQ-untreated subjects on blood or plasma specimens.	4. Serological analyses at 4 times points (baseline, 30,60 and 90 days of study enrollment---with a 7-day window after each time point to complete analyses)

5. Metagenomic next generation sequencing of SARS-CoV-2 isolates detected in subjects	5. Sequence of viral isolates compared to published genomes and community-circulating SARS-CoV-2
---	--

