## 7.4 Description of Statistical Methods

### 7.4.1 General Approach

All data will be summarized using appropriate descriptive statistics, including mean, median, standard deviation, and range for continuous variables and frequency and proportions for categorical variables. Data will also be summarized graphically. Distributional assumptions will be assessed with suitable transformation conducted if indicated. Significance tests will use two-sided Type I error rate of 0.05.

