### 7.4.2 Analysis of the Primary Efficacy Endpoint(s)

Detection of SARS-CoV-2 RNA by PCR will be the primary endpoint and will be compared between treatment groups (prophylaxis vs. no prophylaxis). Positive SARS-CoV-2 will be defined as a binomial variable (i.e., positive SARS-CoV-2 or no positive SARS-CoV-2) and analyzed using Wilcoxon rank analysis. Potential confounders of the primary endpoint will be addressed by using standard statistical matching techniques, such as propensity score matching, and logistical regression to assess for confounding by exposure risk, demographic factors and comorbidities that are known or suspected to affect the likelihood of developing SARS-CoV-2 infection.

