## 7.5 Sample Size

The total sample size will be approximately 350 participants. We do not know in advance how many will opt to take or not take HCQ. The table below provides the detectable difference in positive SARS-CoV-2 rate for different proportions of participants in the treated and control groups. For example, if two-thirds of the sample opt to take HCQ, we will have 80% power to detect a difference in positive SARS-CoV-2 rate of approximately 15 percentage points (e.g., a 35% PCR positivity rate in the control group and a 20% PCR positivity rate in the HCQ group). These calculations assume a two-sided Type I error rate of 0.05. The exploratory endpoints remain independent of enrollment in Group A vs. Group B.

Treatment Group	Control Group	Detectable difference
175	175	0.14
230	120	0.15
260	90	0.17

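### Section 7.4.3 carries the primary endpoint's large-sample Wilcoxon and logistic methods over to hospital admission, ICU admission and death with no rule for sparse events, although the protocol's own figures imply about a quarter of a death

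*Combined protocol and SAP*

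**What the plan says.** Secondary objective 3 (Section 3) concerns the severity of infection. Its endpoints include "Hospital admission rate, ICU admission rate, Mortality rate", together with symptom questionnaires and a respiratory severity score.

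For the yes/no clinical outcomes among these, Section 7.4.3 states: "These binary clinical outcomes will be analyzed in a manner similar to that described above for the primary endpoint". It adds that symptoms will enter as predictors. The method it points to is in Section 7.4.2: the binary outcome is "analyzed using Wilcoxon rank analysis", and confounding is handled by matching (a propensity score is the example given) and by logistic regression on exposure risk, demographics and comorbidities. Section 7.4.1 sets the level: "Significance tests will use two-sided Type I error rate of 0.05".

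Neither section names an exact test, a penalised model, a minimum event count, or a rule that an outcome is only described when events are few. Sections 7.1 and 7.4.1 promise frequencies and proportions for all categorical data, in addition to the tests.

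**The concern.** On a 0/1 variable the Wilcoxon test with tie correction is essentially the chi-square test for two proportions. It relies on a normal approximation that needs a reasonable number of events. A logistic model has no finite estimate for the treatment effect when one group has no events, and an ordinary model with several covariates is unstable when events are few.

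Section 1 gives one severity figure for infected health care workers, and it is low. If death, and possibly admission and ICU stay, occur only once or twice, the plan prescribes a p-value that can look much stronger than the data allow and a model that cannot be fitted. The choice of an alternative would then be made after the data are seen, in an open-label comparison of groups that chose their own treatment.

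**Working it through.** **Inputs**

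- Total size (Section 7.5): "The total sample size will be approximately 350 participants".
- Infection rates (Section 7.5): "a 35% PCR positivity rate in the control group and a 20% PCR positivity rate in the HCQ group".
- Splits, HCQ/control: 175/175, 230/120 and 260/90 (table in Section 7.5), and 275/75 (enrolment caps in Section 4.2.1). The table's control groups all exceed the cap of 75, so all four splits are shown.
- Deaths per infection (Section 1): "An early report of 1700 cases of COVID-19 among health care workers (HCWs) caring for COVID-19 patients in China, included 5 deaths". That is 5/1700 = 0.29%, exact 95% confidence interval 0.10% to 0.69%.
- Admission and ICU rates: not given. Assumed range: 1% to 20% of infections.
- Attrition: not given; taken as zero. Any attrition lowers the counts.

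**The plan's own figure.** Section 7.5 says that "if two-thirds of the sample opt to take HCQ, we will have 80% power to detect a difference" of about 15 points. At 230/120 the pooled rate is (46 + 42)/350 = 0.2514. The standard error is 0.0489 under the null and 0.0509 under the alternative. Power is Φ[(0.15 − 1.96 × 0.0489)/0.0509] = 85.7% (84.7% with Fisher's test). The stated 80% is therefore slightly conservative. It concerns the primary endpoint only; no power or event count is stated for the secondary outcomes.

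**Expected deaths** = (n_HCQ × 0.20 + n_control × 0.35) × 5/1700. The chance of none is (1 − 0.20 × 5/1700)^n_HCQ × (1 − 0.35 × 5/1700)^n_control.

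| HCQ/control | Infections | Expected deaths | Chance of no death | Chance that at least one group has none |
|---|---|---|---|---|
| 175/175 | 96.25 | 0.28 | 75% | 98% |
| 230/120 | 88 | 0.26 | 77% | 99% |
| 260/90 | 83.5 | 0.25 | 78% | 99% |
| 275/75 | 81.25 | 0.24 | 79% | 99% |

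When a group has no death, the crude odds ratio is zero, infinite or undefined. Less favourable inputs change little:

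- 35% infected in both groups: 122.5 × 5/1700 = 0.36 deaths.
- Upper confidence limit of 0.69% at 230/120: 0.60 deaths.
- All 350 infected: 350 × 5/1700 = 1.03 deaths.

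**Large-sample against exact p-values.** Take no event on HCQ and two in controls. Then z = (p_control − p_HCQ)/√[p(1 − p)(1/n_HCQ + 1/n_control) × N/(N − 1)], with p = 2/350. At 260/90, z = 0.02222/0.00923 = 2.41. The exact probability that both events fall in the control group is n_control(n_control − 1)/(350 × 349). In these three splits no other table is as extreme, so this is also Fisher's two-sided p.

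| HCQ/control | Wilcoxon p | Fisher p |
|---|---|---|
| 230/120 | 0.0499 | 14280/122150 = 0.117 |
| 260/90 | 0.016 | 8010/122150 = 0.066 |
| 275/75 | 0.007 | 5550/122150 = 0.045 |

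A half-rank continuity correction hardly matters. At 230/120 the rank statistic lies 230 from its mean, with standard deviation 230/1.9607 = 117.3, so z becomes 229.5/117.3 = 1.956 and p = 0.0504.

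**Admission and ICU, assumed range, unequal splits**

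| Share of infections | Expected events | Chance that a group has none |
|---|---|---|
| 1% to 2% | 0.8 to 1.8 | 66% to 90% |
| 5% | about 4 | 21% to 31% |
| 10% | 8 to 9 | 2% to 7% |
| 20% | 16 to 18 | under 1% |

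**Overall size of the Wilcoxon test** at nominal 0.05, same splits, with a common 25% infection rate: 0.001 to 0.003 at the death rate, 0.033 to 0.042 at 5% of infections, 0.037 to 0.046 at 10%, and 0.047 to 0.049 at 20%.

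**The case against.** The strongest case against has five parts.

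- **Only death is covered by the protocol's figures.** This stands. With 10% to 20% of infections admitted, the unadjusted test is close to its nominal size and a crude odds ratio is usually estimable. An ordinary multi-covariate model would still be thin on 8 to 18 events.
- **The example at the enrolment caps changes no decision.** This also stands. At 275/75, 0.007 and 0.045 are both below 0.05, although the first overstates the evidence about seven-fold. At 260/90 and, narrowly, at 230/120 without a continuity correction, the conclusion at 5% does change.
- **The wording leaves room for an exact version, and counts will be tabulated anyway.** True, but nothing requires the exact version, so the choice stays open until the data are known.
- **Severity does not rest on these three outcomes alone.** Correct: objective 3 also uses questionnaires and a severity score. This limits the damage.
- **Few events do not break propensity matching.** Correct: the propensity model describes who chose HCQ. Sparse outcomes are no reason to abandon confounding control.

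A reader might infer that the planned test produces too many false positives in general. The documents do not support that, because overall size is at or below 0.05 across the range shown. A reader might also infer that the Wilcoxon is blind to harm when events are few. That follows from the 275:75 split and is shared by the exact test: 13 events, all on HCQ, give a Fisher p of 0.079.

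**Conclusion.** The point holds in a limited form. For mortality it rests on the protocol's own numbers: 0.24 to 0.28 expected deaths, a 75% to 79% chance of none, and a 98% to 99% chance that at least one group has none. The planned odds ratio will almost surely not be estimable. This assumes that the Section 7.5 example rates and the Section 1 fatality figure apply; even universal infection would give only about one death.

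For admission and ICU stay it is conditional. If those events also number only a few, the nominal p-value for a one-sided table can be well below the exact one. If they reach 10% to 20% of infections, the unadjusted test is acceptable and only the multi-covariate model is in doubt. Two provisions may lower the counts further: a positive PCR is listed as a reason for early withdrawal or termination (Section 4.6), and serious events are recorded until 30 days after participation ends (Section 6.4).

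This is a worthwhile, inexpensive improvement to the secondary analysis. It does not affect the primary endpoint.

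**What to change.** Amend Section 7.4.3 for hospital admission, ICU admission and death:

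1. Report counts by group with exact 95% confidence intervals, and use Fisher's exact test in place of the Wilcoxon.
2. Report death descriptively and state the expected count in the plan. Exact intervals remain informative with no events: the upper limit is 1 − 0.025^(1/275) = 1.3% for 0 of 275, and 1 − 0.025^(1/75) = 4.8% for 0 of 75.
3. Fit an adjusted model only when events allow, with the minimum count set in advance, and then as a penalised (Firth) or propensity-score-adjusted model. Do not fit an ordinary multi-covariate logistic model to these outcomes. Matching may stay.

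An ordered worst-severity scale is an option but not needed here. Infected against not infected (about 81 of 350 at 275/75) would dominate it, so it would largely repeat the primary comparison.

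The cost is SAP wording, with no new data and no change to sample size or conduct. The downside is that exact tests are conservative, so p-values will be somewhat larger.

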#### 4.2.1.1 Inclusion Criteria

1. Men or women  $\geq 18$  years of age who are UNM HEALTH SYSTEM health care workers and are asymptomatic for known presenting symptoms of SARS-CoV-2:
2. UNMHS HCWs include: MD/DO, NP, RN, and respiratory therapists working in ED, Pediatric ED, Urgent Care, Pediatric Urgent Care or on Covid-19 units. Study PI's will consider study enrollment of HCWs from other settings, for example certain outpatient clinics or inpatient units.
3. Are not positive for SARS-CoV-2 testing
4. Willing and able to comply with survey completion, scheduled visits, treatment plan, and other study procedures
5. Willing and able to provide informed consent

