### **7.3 Analysis Datasets**

The primary analysis data set will consist of positive SARS-CoV-2 outcomes for all enrolled participants. Sensitivity analyses will be conducted using the subset of HCQ participants who complete their entire course of treatment.

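### Baseline IgG status is to be measured in both self-chosen groups but is left out of the primary comparison, where unrecognised prior infection could confound it

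*Combined protocol and SAP*

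**What the plan says.** **Primary comparison.** Section 5.2.2 forms the groups by participants' own choice, and Section 5.2.3 allows a later move from Group B to Group A. Section 7.3 states: "The primary analysis data set will consist of positive SARS-CoV-2 outcomes for all enrolled participants". The one sensitivity set it names is HCQ participants who finish their course. Section 7.4.2 deals with confounding by propensity matching and logistic regression. The factors it names are exposure, demographics and comorbidity.

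**Entry.** No inclusion or exclusion criterion uses serology. The relevant inclusion criterion in Section 4.2.1.1 reads "Are not positive for SARS-CoV-2 testing", with no test type and no look-back period.

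**Serology.** Section 3 lists a between-group comparison of seroconversion as an exploratory objective, with samples at baseline and days 30, 60 and 90. The schedule of activities in Section 5.2.1 has plasma or serum drawn at baseline, and its footnote allows banking for later assay. Section 7.4.3 gives the responder rule, "Positive values will be defined as a four-fold or greater increase in IgG antibody titers compared to baseline", together with descriptive summaries of titers. It states no assay cut-off, no value for titers below the detection limit, and no separate handling of participants already seropositive.

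**Background.** Section 1 says "No acquired immunity to this novel viral infection appears to exist in the human population globally".

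**The concern.** Without randomisation, nothing balances prior infection between the groups. A worker who had an untested, perhaps asymptomatic, infection before enrolment can satisfy the entry criteria and sits in the primary denominator, probably with a lower chance of a positive PCR during 90 days. Prior infection may also be related to the choice to take HCQ, whether through exposure history or through belief about past illness. A variable related to both group choice and outcome is a confounder. This one will be measured, but the plan does not use it for the primary endpoint.

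At stake is the size, and possibly the sign, of a modest estimated effect. Separately, the exploratory seroconversion result could depend on conventions chosen after the titers are known.

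**Working it through.** **1. The plan's own figure.** Section 7.5 gives these inputs: "The total sample size will be approximately 350 participants"; "a 35% PCR positivity rate in the control group and a 20% PCR positivity rate in the HCQ group"; and "These calculations assume a two-sided Type I error rate of 0.05". The table row nearest to two-thirds on HCQ is 230 HCQ and 120 control, for which "we will have 80% power to detect a difference in positive SARS-CoV-2 rate of approximately 15 percentage points".

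- Pooled rate: (120 × 0.35 + 230 × 0.20)/350 = 0.2514.
- Standard error under the null: √[0.2514 × 0.7486 × (1/120 + 1/230)] = 0.0489.
- Standard error under the alternative: √[0.35 × 0.65/120 + 0.20 × 0.80/230] = 0.0509.
- Power: Φ[(0.15 − 1.96 × 0.0489)/0.0509] = 85.7%. It is 82.7% with continuity correction and 84.7% by Fisher's exact test.

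The stated 80% is therefore slightly conservative. Nothing below depends on that gap.

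**2. Effect of prior immunity on the primary comparison.** Let qA and qB be the immune shares in the HCQ and control groups. The documents give neither, so the values below are assumptions. Immune participants are assumed to have no PCR events, which is also an assumption.

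- With no HCQ effect, apparent risk ratio (RR) = (1 − qA)/(1 − qB).
- With the plan's rates, observed difference = 0.35(1 − qB) − 0.20(1 − qA). Power is recomputed as in step 1 with 230 and 120.

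| qA / qB | RR if no HCQ effect | Observed difference at 35% vs 20% | Power |
|---|---|---|---|
| 0 / 0 | 1.00 | 15.0 points | 86% |
| 5% / 5% | 1.00 | 14.25 points | 83% |
| 10% / 10% | 1.00 | 13.5 points | 81% |
| 2% / 5% | 0.98/0.95 = 1.03 | 13.65 points | 80% |
| 2% / 10% | 0.98/0.90 = 1.09 | 11.9 points | 69% |
| 5% / 2% | 0.95/0.98 = 0.97 | 15.3 points | 88% |
| 10% / 2% | 0.90/0.98 = 0.92 | 16.3 points | 92% |

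Equal shares shrink the absolute difference but leave the risk ratio at 0.20/0.35 = 0.571. Removing the immune participants then recovers little power: 0.6 percentage points at 5% and 1.4 at 10%. Unequal shares bias the ratio, and the last two rows show the bias reversing when the imbalance reverses. The 2% / 10% case means about 5 of 230 against 12 of 120 participants.

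**3. Scale against chance.** With the same true rate r in both groups, the 95% chance factor on the risk ratio is exp{1.96 × √[((1 − r)/r)(1/120 + 1/230)]}. This is 1.55 at r = 20% and 1.35 at r = 35%. When HCQ has no effect, the two-sided false-positive rate stays close to 5% for 2% / 5% and rises to roughly 6% to 8% for 2% / 10%.

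**4. The four-fold rule (exploratory).** Assume a detection limit of 10.

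- Undetectable baseline, follow-up titer 20: the ratio is 4.0 if the baseline is set to half the limit (responder), 2.8 at limit/√2 and 2.0 at the limit (both non-responder), and undefined at zero.
- Undetectable baseline, follow-up titer 40 or more: a responder under every non-zero convention.
- Seropositive baseline: 320 to 640 is a ratio of 2, so a boost is missed. A rise from 40 to 160, still under way from an infection before enrolment, is a ratio of 4 and counts as on-study. A stable 320 to 320 is correctly a non-responder.

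**The case against.** Several points on the other side stand:

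- **Serology is exploratory.** The four-fold rule cannot alter the primary result.
- **The baseline titer is more than a divisor.** Section 7.4.3 also plans descriptive summaries. What is missing is any use of baseline status in the primary analysis.
- **The background expects little prior immunity.** If that held for this workforce throughout the 12-month study, the primary bias would be close to nil. But Section 1 also says that infection can be asymptomatic and that health care workers are at increased risk, so unrecognised infection by the time of enrolment cannot be ruled out.
- **The entry criterion may bar anyone with a known positive test.** The gap then concerns only unrecognised infection.
- **The sizes are assumed and mostly lie within chance variation.** Only a marked imbalance matters.
- **Adjusting for exposure may absorb part of the effect.** It is an indirect substitute for a status that will be measured.

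A reader might infer that immune workers gather among those who decline HCQ, so that the drug would look ineffective or harmful. The documents do not support that direction. More heavily exposed workers could be both more often immune and more inclined to take HCQ, which would reverse the bias.

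A reader might also infer that the four-fold rule is wrong for most participants and undercounts seroconversion. For an undetectable baseline it is undefined, which is a different fault: under common conventions only follow-up titers near the detection limit change class. No undercount can be quantified from the documents.

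**Conclusion.** The point holds as an omission in the primary analysis. A plausible confounder of a non-randomised comparison will be measured at baseline in both groups but appears in neither the named adjustment factors nor any sensitivity analysis. The likely size is small if prior infection is rare or balanced. It becomes material if the imbalance is several percentage points: a spurious risk ratio of 1.09 at 2% / 10%, or 0.92 with the shares reversed. These figures rest on assumed immune shares and on immune participants having no PCR events; the documents give neither. The direction cannot be stated in advance.

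The four-fold rule is a lesser, exploratory matter of incomplete definition. The change is worth making because it costs little and would be post hoc if made after results are seen.

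**What to change.** **Section 7.4.2:** add baseline IgG status, positive or negative at a stated assay cut-off, to the propensity and logistic adjustment. Report baseline serostatus by group.

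**Section 7.3:** add a sensitivity analysis of the primary endpoint restricted to participants who are IgG-negative and PCR-negative at baseline. This also covers quasi-separation in the logistic model if no seropositive participant has an event.

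**Section 7.4.3 (exploratory):** report seroconversion among baseline IgG-negative participants by the assay cut-off, with a stated value for titers below the detection limit. Report the four-fold rise separately for those IgG-positive at baseline.

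**Cost:** mainly wording, since the samples are already scheduled. There are three small downsides:

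- The at-risk set in the restricted analyses is slightly smaller.
- Some baseline positives will be false. At an assumed 2% prevalence, 90% sensitivity and 98% specificity, 0.018/(0.018 + 0.0196) = 48% of positives are real. At 99% specificity it is 0.018/(0.018 + 0.0098) = 65%.
- The analyses that use serostatus must wait for the banked samples to be assayed.

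Section 10.1 has samples destroyed after analysis and study completion, so the cut-off and the below-limit convention should be fixed before the assays are run.
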